**Table 6 Objectives and Endpoints for Part 2 – Optional OLE**

Objectives	Endpoints
Exploratory	
Safety	
 
• To evaluate the tolerability and safety of up to 3 years of treatment with basmisanil
 
• Incidence, nature, and severity of AEs and SAEs
 
• Incidence of treatment discontinuations due to AEs
 
• Incidence of laboratory abnormalities based on hematology, clinical chemistry, and urinalysis test results
 
• ECG changes from baseline; incidence of abnormal ECG assessments
 
• Change from baseline in all seizure frequency, duration, and type as reported in a seizure diary by caregivers
 
• Abnormal changes in EEG recordings compared to baseline with a focus on treatment emergent epileptiform abnormalities
 
• Systolic and diastolic blood pressure and heart rate measurements
 
• Suicidality as assessed through questions from selected items adapted from the C-CASA in participants aged 6 years and above
 
• Height, weight, head circumference
 
• Tanner staging over time (in participants aged 9 years and above)
 

Efficacy	
 
• To evaluate the effects of up to 3 years of treatment with basmisanil on core symptom domains of Dup15q syndrome (language and social skills) and daily functioning
 
• Vineland-3: Adaptive Behavior Composite
 

AE = adverse event; C-CASA = Columbia Classification Algorithm for Suicide Assessment; ECG = electrocardiogram; EEG = electroencephalogram; OLE = open-label extension; SAE = serious adverse event; Vineland-3 = Vineland Adaptive Behavior Scales-Third Edition.

**Table 6 Objectives and Endpoints for Part 2 - Optional OLE (cont.)**

Objectives	Endpoints

Efficacy (cont.)
 
 
• To evaluate the effects of up to 3 years of treatment with basmisanil on:           
 
○ Motor function
 
○ Cognition
 
○ Language
 
○ Social skills
 
○ Clinician global impression of severity and change
 
○ Challenging behaviors
 
○ Health-related quality of life of the caregiver
 
○ Caregiver global impression of severity and change
 
 
 
	
 
• Vineland-3: gross and fine motor subdomains
 
• MSEL: gross and fine motor domains
 
• MSEL visual reception domain
 
• Vineland-3 expressive and receptive communication subdomains
 
• MSEL expressive and receptive language subdomains
 
• Vineland-3 play and leisure time and interpersonal relationships subdomains
 
• Dup15q CGI-S and Dup15q CGI-C
 
• ABC-2-C domain scores
 
• PedsQL-FIM
 
• Dup15q CaGI-S and Dup15q CaGI-C
 

PK
 
 
• To characterize the PK of basmisanil and its metabolite M1 [REDACTED]
 
• To evaluate potential relationships between selected covariates and exposure to basmisanil, if appropriate
 
	
 
• Concentration per timepoint for basmisanil and M1
 
• PK parameters as appropriate
 

ABC-2-C = Aberrant Behavior Checklist - Second Edition - Community Version; Dup15q CaGI-C = Dup15q syndrome Caregiver Global Impression of Change scale; Dup15q CaGI-S = Dup15q syndrome Caregiver Global Impression of Severity scale; Dup15q CGI-C = Dup15q syndrome Clinician Global Impression of Change scale; Dup15q CGI-S = Dup15q syndrome Clinician Global Impression of Severity scale; MSEL = Mullen Scales of Early Learning; OLE = open-label extension; PD = pharmacodynamics; PedsQL-FIM = Pediatric Quality of Life Inventory™ Family Impact Module; PK = pharmacokinetics; qEEG = quantitative EEG; Vineland-3 = Vineland Adaptive Behavior Scales-Third Edition.

**Table 6 Objectives and Endpoints for Part 2 – Optional OLE (cont.)**

Objectives	Endpoints
PD	

 
• To evaluate maintenance of EEG PD effect over the treatment period
 
	
 
• qEEG beta-band power
 

PK relationship to efficacy, safety, and PD	

 
• To evaluate potential relationships between drug exposure and the efficacy, safety and PD of basmisanil
 
	
 
• Relationship between plasma concentration or PK parameters for basmisanil or M1 (if appropriate) and efficacy, safety, and PD endpoints
 

EEG = electroencephalogram; OLE = open-label extension; PD = pharmacodynamics; PK = pharmacokinetics; qEEG = quantitative EEG.

## 4. **STUDY DESIGN**

### 4.1 **OVERALL DESIGN**

An overview of the study design is provided in Section 1.2.

This study consists of two parts. Part 1 is a multi-center, randomized, double-blind, placebo-controlled, parallel group study to evaluate the safety, efficacy, and pharmacodynamics of 52 weeks of basmisanil treatment in children and young adolescents aged 2 to 14 years with Dup15q syndrome. Part 2 is a 2-year optional OLE on basmisanil.

In Part 1, approximately 90 participants will be randomized 2:1 to receive oral treatment with either basmisanil or placebo for 52 weeks (BID on the first day of treatment in the clinic (Day 1) and three times a day [TID] for the remaining study duration; see Section 4.3 for justification).

Randomization will be stratified by age group (2 to 5 years vs. 6 to 14 years), number of copies of the 15q11.2-q13.1 region (3 copies vs. 4 copies), and epilepsy (presence vs. absence). All participants who have completed 52 weeks of treatment in Part 1 will be offered the option to roll over directly to the OLE (Part 2) without completing the follow-up visit in Part 1 (no treatment gap). No new patients will be enrolled in the OLE. All participants in Part 2 will receive oral treatment with basmisanil for approximately 2 years (see Section 4.3 for justification).

#### **Assessments for Part 1 and Part 2**

Efficacy, safety, PK, and PD assessments will be conducted throughout the study, as detailed in the SoA (Section 1.3). Participants will be closely monitored on the Day 1, Day 2 (Part 1) and Day 366 (Part 2) clinic visits, during which PK samples will be

[figure not shown]
obtained, and EEG recordings and relevant safety assessments will be performed (see SoA in Section 1.3).

In Part 1, recruitment will be staggered as follows (see Figure 2):

- By age [REDACTED] to assess safety in participants aged 6 to 14 years before exposing participants aged 2 to 5 years, see Figure 2.
- By presence or absence of epilepsy to assess the effect of basmisanil on seizures before enrolling participants without epilepsy (for rationale see Section 4.2.1).

The study consists of *two* stages:

**Figure 2 Staggered Enrollment in Part 1**

IMC = Internal Monitoring Committee; N = number of participants; SOC = Scientific Oversight Committee; y = years.

Staggered enrollment by age and presence or absence of epilepsy will be implemented as follows:

- **Stage 1:** Participants between ages 6 and 14 years (*inclusive*) with epilepsy will be enrolled.  
Data from a minimum of 9 participants enrolled in Stage 1 will be reviewed by an IMC + SOC as described in Section 4.1.2.2 prior to opening recruitment to participants aged 2 to 5 years and participants without epilepsy into Stage 2.

- **Stage 2:** *The remaining participants aged 2 to 14 years with or without epilepsy will be enrolled following IMC + SOC recommendation to reach a total sample size of approximately N=90.*

*Data from participants enrolled into Stage 1 and 2 will be included in periodic reviews by the IMC + SOC and a first interim analysis will be performed when approximately N=24 participants reach 4 weeks of treatment, as described in Section 4.1.2.2.*

*Overall, the study aims to enroll a minimum of approximately one-third of participants aged 2 to 5 years and a maximum of approximately one-fifth of participants aged 12 to 14 years.*

### **Treatment Groups and Duration**

Treatment with basmisanil or placebo granules, packaged in stick-packs, will be administered orally within 30 minutes after the start of a meal (see Section 6.4).

**Table 7 Starting Doses According to the Age of the Participants:**

Age Group	Starting Dose (mg)	Duration (Weeks)
2 to 5 years	100	52
6 to 11 years	100	52
12 to 14 years	100	52
15 to 17 years	100	52

*In Part 1, the starting dose is determined according to the participant's age at the time of signing of the Informed Consent Form, and maintained for the 52-week treatment duration.*

*In Part 2, the starting dose, dosing regimen and age-defined dose groups are initially the same as for Part 1 (Day 2 and onwards) and determined based on the participant's age at the start of Part 2 (Day 366 visit). During Part 2, the dose will be adjusted according to the participant's actual age. If applicable, the dose must be changed at the latest on the first dispensation visit after a participant moves into a different age group.*

*Dose and dose regimen for participants aged 15 to 17 years are predicted to be similar to what has been determined as the starting steady state regimen in Part 1 for 10 to 14 years old*

#### **4.1.1 Length of the Study**

The *planned* total study duration is approximately 61 weeks for participants who participate in Part 1 only and 165 weeks for those participating in Parts 1 and 2, divided into the following periods:

- Screening period of *up to* 5 weeks (Day -35 to Day -2), which may overlap with the baseline period (Day -7 to Day -1)
- Double-blind 52-week treatment period (Day 1 to Day 365)
- *Optional OLE treatment period of approximately 2 years/104 weeks (Day 366 to Day 1095/Year 3)*
- Follow-up period of approximately 4 weeks (*Part 1: Days 365 to 395 or Part 2: Days 1095 to 1125*)

The screening period starts once the first screening assessment is performed (not with signing the Informed Consent Form [ICF]). *All screening assessments required to confirm participant's eligibility for study participation need to be completed with results available before the Baseline visit.* The Baseline visit can be done anytime between Day - 7 and Day -1.

#### **4.1.2 Internal Monitoring Committee and Scientific Oversight Committee**

##### **4.1.2.1 Administrative Structure**

##### **Internal Monitoring Committee**

A Sponsor IMC will be responsible for regular reviews of accumulating safety, tolerability, and [REDACTED] in terms of tolerability and exposure. The IMC will consist of internal Sponsor experts representing Clinical Pharmacology, Pharmacometrics, Clinical Science, Drug Safety, Statistics, as

well as Biomarkers. Attendance at IMC meetings will be determined by the purpose of the IMC meeting; not all members are expected to be required for all meetings.

IMC members will review unblinded aggregated information as part of all reviews and interim analyses, i.e., summary information by treatment arm. As required by their functional expertise, selected IMC members (e.g., clinical pharmacology, drug safety) may be unblinded also at a participant level.

Individual study team members outside the IMC required to prepare information for IMC review will be unblinded to the treatment assignment of individual participants. Access to treatment assignment information will follow the Sponsor's standard procedures.

### **Scientific Oversight Committee**

*During Part 1 of the study, an SOC will help monitor safety and tolerability data until all participants have completed or were prematurely withdrawn from Part 1.*

*Specifically, the SOC will help interpret any changes in seizure status and/or EEG findings in this patient population, to ensure that the study in its current form does not pose unacceptable safety risks to participants. The SOC will consist of one or more external neurologist/epileptologist with expertise in pediatric epilepsy in neurogenetic disorders and who is not an Investigator in this study. The SOC members will also review unblinded aggregated information and may be unblinded at the participant level if required.*

A separate IMC+SOC agreement will include additional details on membership and procedures.

#### **4.1.2.2      Review Objectives and Procedures**

*During Part 1, the IMC will perform periodic reviews of all available PK exposure, safety, and tolerability data, including up to two interim analyses as described below. As part of these reviews, the SOC may be consulted on the interpretation of safety and tolerability data if required. "IMC+SOC" is used to refer to these reviews with the focus as described below.*

##### **Periodic reviews during enrollment of the first 24 participants in Part 1 Stages 1 and 2:**

*The objectives of the IMC+SOC periodic reviews of the initial PK and safety data are to:*

(2) confirm that data support opening enrollment into Stage 2.

The clinical pharmacologist, supported by a pharmacometrist, will review exposure data on a continuous basis. [REDACTED]

Once a minimum of 9 participants have completed their first 4 weeks of dosing in **Stage 1**, the IMC+SOC will perform a review of all available PK exposure, safety, and tolerability data. Based on this review, the IMC may [REDACTED]

*Periodic reviews of PK and safety data by the IMC+SOC will continue throughout the course of the study.*

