**3. Modification of staggered recruitment (see Section 4.1 including Figure 2)**

- The inclusion criteria for Stage 2 have been partially relaxed to allow inclusion of all participants meeting study eligibility criteria irrespective of their age or epilepsy diagnosis. Staggered recruitment thus occurs in two stages, instead of 3 previously.
- The interim analysis will be performed when approximately 24 participants recruited in Stages 1 and 2 reach 4 weeks of treatment, with a minimum of 9 participants aged 2-5 years.

The staggered approach by age and by presence or absence of epilepsy remains (see Section 4.1). The change, however, allows recruitment of both younger patients and patients without epilepsy simultaneously in Stage 2, rather than consecutively. There is no evidence for differences in epilepsy severity or presentation, nor a mechanistic rationale suggesting a different pro-epileptic risk with basmisani treatment between age groups. The theoretical risk of worsening of seizures is related to the mechanism of action of basmisani and should thus occur at a high frequency (Type A event). As such, the safety profile of basmisani can be adequately assessed based on data from 9 participants aged 6 to 14 years presenting with epilepsy to safely ungate enrollment in Stage 2. Similarly, the interim analysis performed on approximately 24 participants recruited in Stages 1 and 2, with a minimum of 9 participants aged 2 to 5 years, will allow adequate evaluation of the overall safety profile of basmisani in individuals representative of the study population. These changes therefore do not affect individual participants' safety and monitoring is in place at all times throughout the study.

The impact of the changes on staggered recruitment is anticipated to be significant. In fact, patients without epilepsy represent about 40% of the Dup15q population (see Section 2.2.1) and their inclusion opens earlier participation to a larger pool of patients. This is expected to accelerate decision-making in Study BP42992. A timely confirmation of age-dependent doses based on the safety and PK data by the Internal Monitoring Committee (IMC) + Scientific Oversight Committee (SOC) (see Section 4.1.2.2) is essential to maximize the number of participants who receive study treatment doses that reach the targeted exposures as early as possible in this

study: the target exposures are anticipated to offer the greatest likelihood of prospective benefit.

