## **6. TREATMENTS**

Study treatment is defined as any investigational product (including placebo) or marketed product intended to be administered to a study participant according to the study protocol.

The investigational medicinal products (IMP) for this study are basmisanil and placebo. *Appendix 6* identifies all IMPs and auxiliary medicinal products (AxMPs)/non-investigational medicinal products (NIMPs). All IMPs required for completion of this study will be provided by the Sponsor.

Cases of overdose, medication error, drug abuse, or drug misuse, along with any associated AEs, should be reported as described in [Appendix 2](#), Section 5.2.

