## **6.3 MEASURES TO MINIMIZE BIAS: RANDOMIZATION AND BLINDING**

### **6.3.1 Method of Treatment Assignment**

All participants will be centrally randomized to study treatment using an Interactive Voice/Web Response System (IxRS). Before the study is initiated, the telephone number and call-in directions for the IVRS and/or the login information and directions for the IxRS will be provided to each site.

Randomization will be stratified by

- Age group (2 to 5 years vs. 6 to 14 years)
- Number of copies of the 15q11.2-q13.1 region (3 copies vs. 4 copies)
- Epilepsy (presence vs. absence)

*In Part 2 all participants are assigned to receive open-label basmisanil, regardless of their treatment assignment in Part 1.*

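### The review that opens Stage 2 counts 9 participants across both arms, so about 6 on basmisanil, and no readable text sets a floor on the number treated

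*Combined protocol and SAP*

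**What the plan says.** Stage 1 enrolls participants aged 6 to 14 years with epilepsy. Section 4.1 sets the condition for moving on: "Data from a minimum of 9 participants enrolled in Stage 1 will be reviewed by an IMC + SOC" before recruitment opens to children aged 2 to 5 years and to participants without epilepsy. Section 4.1.2.2 gives the timing: "Once a minimum of 9 participants have completed their first 4 weeks of dosing in" Stage 1, the Internal Monitoring Committee (IMC) and Scientific Oversight Committee (SOC) review all available exposure, safety and tolerability data.

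Neither section says how many of the 9 must be on active drug. Section 4.1 states that "approximately 90 participants will be randomized 2:1 to receive oral treatment with either basmisanil or placebo for 52 weeks", with no separate ratio for Stage 1. Section 6 counts placebo as treatment: "Study treatment is defined as any investigational product (including placebo").

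The reason for the number is in the Version 3 amendment rationale, item 3, which supports the current two-stage design. It says the safety profile of basmisanil "can be adequately assessed based on data from 9 participants aged 6 to 14 years presenting with epilepsy". Its argument is that seizure worsening, being tied to the mechanism, "should thus occur at a high frequency (Type A event"). It gives no rate and does not mention the placebo share.

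**The concern.** The review is meant to judge a risk of basmisanil, and only treated participants carry direct information on it. Section 2.3.1.2 says the risk of exacerbating or triggering seizures in this syndrome is not established, because earlier trials excluded people with epilepsy. Section 4.2.1 puts the lower age limit of prior pediatric experience at 6 years. The Stage 1 review is therefore the step before a new age group and participants without epilepsy are exposed.

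A minimum of 9 that includes placebo participants gives less assurance than the number suggests, and chance in the allocation can reduce it further. Without a floor on the treated count, the condition could be met with 5 treated, or with 4 under larger blocks.

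**Working it through.** **Inputs.** Minimum of 9 with 4 weeks of dosing (Sections 4.1 and 4.1.2.2). Allocation 2:1 (Section 4.1). Stratification by age group, copy number and epilepsy (Section 6.3.1); age group and epilepsy are fixed in Stage 1, so only copy number, with two levels, is active there. Not in the documents and therefore assumed: permuted blocks of size 3 or 6, and the share of Stage 1 participants with 4 copies (85%, varied below). The plan gives no derivation for 9, so there is no figure of its own to reproduce.

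**Expected number treated.** 9 × 2/3 = 6, leaving 3 on placebo.

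**Blocks of 3.** Let *a* be the number in one copy-number stratum. If *a* is a multiple of 3, all blocks are complete and exactly 6 are treated. Otherwise one stratum has one participant in an open block and the other has two.

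- The single participant is on placebo with probability 1/3.
- The pair contains only one treated participant with probability 2/3.
- Both together give 5 treated, with probability 1/3 × 2/3 = 2/9.

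With 85% having 4 copies, the 3-copy count is a multiple of 3 with probability 0.85^9 + 84 × 0.15^3 × 0.85^6 + 84 × 0.15^6 × 0.85^3 = 0.2316 + 0.1069 + 0.0006 = 0.339. So P(5 treated) = 2/9 × (1 − 0.339) = 0.147.

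**Blocks of 6.** The same enumeration over the open blocks gives P(5 or fewer treated) = 0.230.

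**Sensitivity.** The number treated ranges from 5 to 7 with blocks of 3 and from 4 to 8 with blocks of 6. For 4-copy shares from 60% to 90%, P(5 or fewer) runs from 12.6% to 15.3% with blocks of 3 and from 22.5% to 23.9% with blocks of 6. With unrestricted 2:1 randomization it would be 35%.

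**What zero events would exclude.** The one-sided 95% upper bound is 1 − 0.05^(1/n):

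| Treated (n) | Upper bound |
|---|---|
| 5 | 1 − 0.05^(1/5) = 45.1% |
| 6 | 1 − 0.05^(1/6) = 39.3% |
| 9 | 1 − 0.05^(1/9) = 28.3% |

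**Chance of seeing at least one event.** This is 1 − (1 − p)^n, for assumed true rates p:

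| True rate | 6 treated | 9 treated |
|---|---|---|
| 10% | 46.9% | 61.3% |
| 20% | 73.8% | 86.6% |
| 30% | 88.2% | 96.0% |
| 40% | 95.3% | 99.0% |
| 50% | 98.4% | 99.8% |

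These figures count any event as a signal. Every Stage 1 participant has epilepsy, so background seizures would make attribution harder than the table implies.

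**The case against.** The strongest reply is that the rationale expects a frequent effect. At true rates of 40% to 50%, having 6 rather than 9 treated lowers the detection chance by only about 1 to 4 points. That is correct as far as it goes. But no rate is stated, and at 10% to 20% the loss is 13 to 14 points.

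Second, the review is a judgement on all available data, not a zero-event rule. Nine is a minimum, the placebo participants help to separate background seizures from drug effect, and periodic reviews and individual stopping rules continue. This stands, and it is why the point is an improvement and not a defect that blocks the trial.

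Third, parts of Section 4.1.2.2 are redacted, Figure 2 is not shown, and Section 4.1.2.1 refers to a separate IMC+SOC agreement. A number on active drug may sit in any of these. This also stands, so absence can be claimed only for the readable text.

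Four stronger readings are tempting, and the documents do not support them:

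- **That the protocol claims 9 were treated.** It does not. The rationale speaks of data from 9 participants and the 2:1 ratio is stated openly. The overstatement is an inference, not a contradiction.
- **That blinding hides the shortfall.** The ratio causes it. Section 4.1.2.1 gives the IMC and SOC unblinded aggregate data, so they will see how many were treated.
- **That the minimum of 9 aged 2 to 5 years is a second condition on exposure.** In Section 4.1.2.2 it triggers the first interim analysis; those children have already been treated for 4 weeks, and enrollment continues meanwhile. The same counting (about 6 treated) can be noted there, no more.
- **That 9 treated participants are needed.** No figure in the documents makes 9 sufficient and 6 not. An expected 9 treated would take 9 ÷ (2/3) = 13.5 randomized, a delay the sponsor may reasonably decline.

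**Conclusion.** The point holds in a limited form. The condition for opening Stage 2 counts both arms, the expected number on basmisanil is 6, and the readable text allows fewer. The chance of 5 or fewer is about 15% with blocks of 3 and 23% with blocks of 6; both figures rest on assumed block sizes and an assumed copy-number mix. A clean result in 6 treated leaves true rates up to about 39% open, and in 5 treated up to about 45%. Whether that matters depends on the true event rate, which the documents do not give: little is lost if it is 40% or more, and a material amount if it is 10% to 20%.

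**What to change.** In Sections 4.1 and 4.1.2.2, keep the minimum of 9 and add: of whom at least 6 have received basmisanil for 4 weeks. The IMC, already unblinded, makes the count and does not disclose it to blinded staff. Because 9 is already a minimum, a review at a later count need not be explained to sites.

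In the amendment rationale, say that the assessment rests on about 6 treated participants, and state the event rate it is meant to detect. Where Section 4.1.2.2 sets the minimum of 9 aged 2 to 5 years for the first interim analysis, note that about 6 of them would be on basmisanil.

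If the IMC+SOC agreement or redacted text already holds a floor on the treated count, a statement to that effect is enough.

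The cost is small. Total sample size, analysis and visits are unchanged. Stage 2 opens later only when fewer than 6 of the first 9 are on basmisanil. With blocks of 3 the delay is then one participant, because every open block has only active assignments left. With blocks of 6 it is usually one or two.
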